## **Study Protocol**

### **1) Abstract of the study**

The purpose of this research is to conduct a pilot study of a decision support intervention for young adults with early psychosis who are participating in early intervention services, also known as coordinated specialty care (CSC).

We will utilize a single-group, pre-post, convergent mixed methods design to explore whether and how the intervention addresses decision-making needs. The impact of the intervention on secondary outcomes (e.g., engagement in the program) will also be assessed. Additionally, we will evaluate the feasibility of research and intervention procedures, and the acceptability of information and support from the interventionist.

### **2) Protocol Title**

Facilitating Emerging Adult Engagement in Evidence-Based Treatment for Early Psychosis through Peer-Delivered Decision Support Part 2

### **3) Sponsor / Funding**

This study is funded by the National Institute of Mental Health under award number K08MH116101

### **4) IRB Review History**

This study is a follow-up study to another protocol previously reviewed by the Temple IRB (protocol # 25075).

### **6) Objectives**

The purpose of this study is to evaluate a decision support intervention with emerging adults participating in CSC services. A peer specialist (i.e., trained mental health provider with lived experience of a mental health

condition) or other staff person at the participating CSC programs will serve as “decision coaches” to participants to help them make decisions about their care. It is hypothesized that participants will experience a reduction in decision-making needs after participating in the intervention, and that study and intervention procedures will demonstrate feasibility and acceptability.

## **7) Background**

Service disengagement among emerging adults with early psychosis (i.e., premature treatment drop-out) is a prevalent problem, with recent estimates between 20-40%. This is particularly concerning given that service disengagement during early psychosis is a risk factor for relapse, persistent symptoms, and poorer prognosis. Further, as emerging adulthood is characterized by key developmental milestones, young people who do not receive appropriate services during this time are at greater risk for health problems and poorer functional outcomes as they age. As such, service disengagement is a performance indicator for evaluating the quality of early psychosis care. While some CSC programs demonstrate relatively low rates of disengagement, others using similar approaches have had more retention difficulties, suggesting that current strategies are not sufficient to address disengagement in all contexts. Especially needed are interventions that promote early engagement (i.e., help-seeking, appointment attendance, engagement in treatment processes) to foster long-term retention and, thus, better outcomes.

Research suggests that decision support may be a particularly efficacious approach for increasing service engagement. First, a number of modifiable treatment decision-making needs (e.g., knowledge deficiencies, lack of social support) contribute to decisional conflict, which, in turn, is associated with discontinuance of chosen options and decisional regret. Second, studies demonstrate that decision support interventions that address these decision-making needs are associated with increased service engagement.

The effectiveness of decision support sets the stage for the development and preliminary analysis of a decision support intervention to facilitate treatment decision-making and enhance early CSC engagement.

## **8) Setting of the Human Research**

Recruitment will occur at Horizon House, Inc., CMSU Behavioral Health and Developmental Services (CMSU), and On My Way CSC programs (i.e., PEACE, CMSU, On My Way) that serve emerging adults with early psychosis. Participants will receive the study intervention at the CSC program from which they were recruited. Research interviews will occur at Temple University, in a conference

room at [name], or at an agreed upon location at the CSC programs.

**In the event that in-person interactions with participants are prohibited due to COVID-19, recruitment, research interviews, and intervention meetings will be conducted remotely via telephone or videoconference (depending on participants' preferences). We will use a HIPAA-compliant version of Zoom for all videoconference meetings.**

## **9) Resources Available to Conduct the Human Research**

We will recruit and collect data from 20 individuals enrolled in the CSC programs who will participate in the intervention. Given that this study's purpose is to collect preliminary data about the intervention's impact on decision-making needs, the sample size is based on pragmatics rather than power, consistent with recommendations for pilot studies. We used the current rate of enrollment at the CSC program and a conservative estimate of study enrollment of 40% to arrive at the projected N.

Research staff for this study include the research assistant, the decision coaches at each of the CSC programs, and PI. The research assistant will dedicate at least 20 hours per week to recruitment and data collection during the study period. The decision coaches are also expected to dedicate at least 10 hours per week delivering the intervention, documenting contacts with participants, and participating in supervision via videoconference with the PI. The PI will dedicate at least 10 hours per week overseeing and managing the implementation of the study, supervising project staff, analyzing data, and completing other project tasks as needed.

Research staff for this study have received extensive training, including completion of the CITI social and behavioral health human subjects training. During weekly staff meetings, the research team will discuss ongoing issues regarding the research to ensure procedures are followed and issues are addressed appropriately.

Research staff have private, furnished office spaces at Temple University with access to Internet jacks, telephones, lockable file cabinets, teleconference equipment, and standard office equipment and supplies to facilitate research-related activities.

The CSC programs are equipped with a large workspace for employees that includes Internet jacks, telephones, lockable file cabinets, and standard office equipment and supplies. They have conference areas with teleconference capability that will be available for recruitment as well as private rooms that will be available for intervention meetings, telephone calls, and research interviews with participants.

## 10) Prior Approvals

Review of this research is also required by the IRB for the City of Philadelphia.

## 11) Study Design

### a) Recruitment Methods

Recruitment will occur at Horizon House, Inc., CMSU Behavioral Health and Developmental Services, and On My Way's programs (i.e., PEACE, CMSU, On My Way) that serve emerging adults with early psychosis. Recruitment strategies that will be utilized to enroll participants in the study include distributing recruitment materials (e.g., study flyers, recruitment video), and completing site presentations. Recruitment materials will be provided to study sites for distribution to potential participants, and will be posted to our lab website and social media platforms. Additionally, we will also collaborate with CSC staff members who will provide information about the study to potentially eligible individuals, and the research assistant will conduct follow ups with those interested in participation for screening.

### b) Inclusion and Exclusion Criteria

The research assistant will determine eligibility in person at the CSC programs or over the telephone/videoconference by using a screening questionnaire with study criteria questions. Screenings conducted at the CSC programs will be conducted in a private room. Screen failures will be notified that they are ineligible for the study, but that this will not have an impact on their ability to continue to access CSC services. All information/materials collected during screening will be stored in a locked office in a locked filing cabinet and within password-protected and encrypted electronic files.

*Inclusion criteria* are: 1) 18-30 years of age; 2) experiencing early psychosis, defined as psychosis lasting 18 months or less between the time when threshold symptom criteria were reached (as determined by the admitting CSC program assessor) and the date of CSC program enrollment; 3) able to speak/understand English; 4) able to provide informed consent as assessed by research staff; and 5) enrolled in the CSC program for any period of time.

*Exclusion criteria* are: having a legal guardian or diagnosis of dementia, delirium, or intellectual disability as determined by the admitting CSC program psychiatrist. No individuals from special populations will be included.

### **c) Local Number of Subjects**

The research assistant will recruit 20 individuals enrolled in the CSC programs to participate in the decision support intervention.

### **d) Study Timelines**

Participants will complete two research interviews (approximately 1.5 hours for the baseline assessment and 2 hours for the post-intervention assessment). Between these two research interviews, they will participate in the study intervention on a weekly or biweekly basis for approximately 1-3 months, and repeat one of the measures that was completed during the baseline assessment (which is expected to take about 10 minutes) (see Procedures section below). Intervention meetings are expected to last 45-60 minutes each. We expect to enroll 2-3 participants per month, and estimate that recruitment and data collection will end in January 2022. Data analysis and reporting is expected to be completed by April 2023.

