## **Procedures Involved in the Human Research**

Screening and recruitment will be ongoing through January 2023. Participants will complete a baseline assessment with the research assistant prior to engaging in the decision support intervention. During the study period, participants will engage in the experimental decision support intervention and will maintain access to other services and supports normally available to them through the CSC program (e.g., medication, therapy). The PI will assess when the participant has determined what

decision they would like to work on with the decision coach via contact notes and supervision sessions. The PI will notify the research assistant when this determination has been made, and the research assistant will contact the participant at that time to have them complete the Decisional Conflict Scale a second time. Participants will not be offered additional payment for completing this measure at this time point. Upon completion of the intervention, participants will complete a post-intervention assessment with the research assistant. At post-intervention, participants will be asked to provide permission to audio-record responses to qualitative questions that are part of the qualitative assessment of decision-making needs and acceptability measure. Participants must provide permission to audio-record these portions of the research interview in order to participate in the study. At baseline and post-intervention, the study team will reach out to participants' psychiatrists/therapists in order to have them complete a questionnaire (Service Engagement Scale). A schedule of assessments collected at each time point is presented in Table 1.

	Table 1. Assessment Schedule		
	Baseline	During Intervention	Post-Intervention
Demographics/Clinical characteristics	X		
Multi-dimensional Scale of Perceived Social Support	X		X
Control Preference Scale	X		X
Perceived Involvement in Care Scale	X		X
Birchwood Insight Scale	X		X
Recovery Assessment Scale	X		X
Internalized Stigma of Mental Illness Scale	X		X
Empowerment Scale	X		X
Decision Self-Efficacy Scale	X		X
Service Use and Resource Form for Monthly Items	X		X

Brief Adherence Rating Scale	X		X
Intent to Attend Measure	X		X
Service Engagement Scale	X		X
Decisional Conflict Scale	X	X	X
Working Alliance Inventory	X		X
Intentional Peer Support Scale			X
Satisfaction with Decision Scale			X
Qualitative Measure of Decision-Making Needs			X
Acceptability Measure			X

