Decision coaching, a process of non-directive support by a trained but neutral individual, is used to facilitate treatment decision-making through assessment of decision-making needs and delivery of specific intervention components to address them. These components may include facilitating access to information, clarifying values, helping a person obtain the needed support to make a decision, and screening for implementation barriers. Following standards of practice for decision coaching, the decision coach will evaluate individuals' decision-making needs and provide coaching tailored to these needs via telephone/videoconference or in face-to-face meetings. Individuals will be invited to speak with the decision coach as long and as many times as are necessary to make a treatment decision; however, it is expected that participation in the intervention will last approximately 3 months and it is suggested that individuals participate in the intervention on a weekly or biweekly basis. Participants will be asked to provide permission to audio record intervention meetings so that fidelity may be assessed. Participants may opt out of audio recording of intervention sessions and will still be able to participate in the intervention.

The research assistant will routinely administer an adverse events checklist at each study visit, and the decision coach will monitor for adverse events during each intervention meeting. If an adverse event occurs during a participant's participation in the study, the interventionist or research assistant will facilitate participants' access to prompt medical or professional care as appropriate, document the event on an adverse event reporting log, and immediately submit documentation of the event to the IRB and NIMH as appropriate.

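### Do the conflicting end dates (January 2022 and January 2023) cost the paired DCS analysis 2-9 of its 20 participants?

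*Combined protocol and SAP*

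**What the plan says.** Section 11 d) Study Timelines states "We expect to enroll 2-3 participants per month" and gives an "estimate that recruitment and data collection will end in January 2022". It adds: "Data analysis and reporting is expected to be completed by April 2023". Between the two research interviews, participants are in coaching: "they will participate in the study intervention on a weekly or biweekly basis for approximately 1-3 months".

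The Procedures section gives a different year: "Screening and recruitment will be ongoing through January 2023". It ties the final assessment to the participant's own course: "Upon completion of the intervention, participants will complete a post-intervention assessment with the research assistant". On the length of coaching it says "it is expected that participation in the intervention will last approximately 3 months", and it offers sessions "as long and as many times as are necessary to make a treatment decision".

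Section 9 (Resources) sets the target at 20 people from whom data will be collected, a number chosen on practical grounds and not from a power calculation. The Statistical Analysis Plan compares DCS subscale scores before and after the intervention with a paired t-test. Section 11 e) lists retention among the feasibility data. No section gives a separate date for the last post-intervention assessment.

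**The concern.** Two current statements about the end of recruitment differ by a year, and the obvious repair does not work. If Study Timelines read January 2023, recruitment and data collection would close in the same month, yet someone enrolled that month still has one to three months of coaching before the final DCS.

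If data collection really stopped then, those still in coaching would have no second score and would drop out of the paired t-test. They could also be counted as lost in the retention figures. Because coaching lasts until a decision is made, a calendar cut-off would tend to remove slower deciders. If data collection ran on instead, it would end in about February to April 2023, close to the April 2023 reporting date. In a pilot of 20, the loss of up to 9 pairs would be noticeable.

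**Working it through.** **Inputs.** Enrolment 2-3 per month and coaching 1-3 months (section 11 d); coaching about 3 months (Procedures); 20 participants (sections 9 and 11 c); two-week transcript review (section 18). The recruitment start date is not given, and the target of 20 cannot be re-derived because the programs' enrolment rate is not stated.

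**Step 1: the count under a hard stop.** Number still in coaching = monthly rate × months of coaching, assuming enrolment continues right up to the close.

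| Coaching | 2 per month | 3 per month | Pairs left of 20 |
|---|---|---|---|
| 1 month | 2 | 3 | 18 or 17 |
| 2 months | 4 | 6 | 16 or 14 |
| 3 months | 6 | 9 | 14 or 11 |

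The range of 2-9 is therefore correct arithmetic on its assumptions.

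**Step 2: what it would cost.** The 95% CI half-width for mean change, in SD of the change, is t(0.975, n−1)/√n: 0.468 at n = 20, 0.497 at n = 18 and 0.672 at n = 11. That is 6% wider (0.497/0.468 = 1.06) to 44% wider (0.672/0.468 = 1.44). At an assumed 80% power and two-sided 5%, the detectable change is 0.66, 0.70 and 0.94 SD respectively. Selection of faster deciders would shift the mean by only 0.02-0.06 SD, assuming coaching times uniform on 1-3 months and a correlation of 0.3-0.5 between coaching time and DCS change.

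**Step 3: does the plan contain a hard stop?** Four statements bear on it:

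- The closing date in Study Timelines is worded as an estimate.
- Section 9 has data collected from 20 individuals.
- The Procedures section times the final assessment by completion of coaching, not by the calendar.
- The Procedures section leaves the length of coaching open.

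None of these cuts anyone off, and the last three point the other way.

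**Step 4: does enrolment run to the close?** Twenty participants take 20/3 = 6.7 to 20/2 = 10 months. For the 20th to enrol at the end of January 2023, recruitment would have to start in about April to July 2022. If January 2022 is an older estimate of the end, recruitment was due to be open by then. Even a start on 31 January 2022 brings in the 20th participant by about 20 August 2022 (3 per month) or 30 November 2022 (2 per month). With 3 months of coaching, those pending on 31 January 2023 are the people enrolled after 31 October 2022: none at 3 per month, and 2 × 1 = 2 at 2 per month.

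**Step 5: month-level dates.** If participants enrol at the start of a month and data collection closes at the end of one, each has one more month: 2 × 0 = 0 to 3 × 2 = 6 pending, even under a hard stop.

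**Step 6: the April 2023 date.** For a participant enrolled on 31 January 2023, coaching of 1, 2 or 3 months ends on 28 February, 31 March or 30 April, leaving 61, 30 or 0 days to 30 April. After the 14-day transcript review, 47, 16 or −14 days remain. Only the last possible enrollee with the full three months overruns. The review concerns interview transcripts, so it does not delay the DCS t-test. If January 2022 is the right end date, about 15 months remain and there is no pressure.

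**The case for a change.** The strongest case for acting is that the contradiction is certain, the one-word repair leaves it half in place, and the remedy is cheap: separate dates for last enrolment and last assessment, plus one sentence on anyone still in coaching at the close. The arithmetic uses the plan's own rate and duration. Without a rule, an administrative close could be mistaken for drop-out in a study where retention is itself an outcome.

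Part of this stands. The dates do conflict, no last-assessment date is given, and the two descriptions of coaching length are worded differently. They can be read together, as a range and an expected duration, but the two sections should be reconciled when the text is next edited; this review does not choose between them. What does not stand is the step from an inconsistent date to lost data. That step needs a cut-off the plan never sets, and the requested sentence would govern an event the plan does not foresee. If a few participants were still in coaching when the team closed the study, an analyst preparing the CONSORT-style flow would ordinarily show them separately from withdrawals.

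**Conclusion.** The date conflict is real but clerical, and it sits in planning estimates. Followed as written, the plan enrols 20 people, assesses them when coaching ends, and applies the paired t-test to those with both scores. The calendar removes no one.

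The loss of 2-9 participants (11-18 pairs, an interval 6-44% wider) arises only if data collection is cut off with recruitment and enrolment is still running at 2-3 per month at that moment. The documents state no such cut-off. Relaxing the timing alone lowers the count to 0-6 or 0-2. The pressure on April 2023 assumes that 2023 is the correct year, and at worst it delays the report on the last transcripts. The precision figures also have no target to miss, since the sample size was not based on power.

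This conclusion rests on reading the January dates as estimates, which is how Study Timelines words its own, and on the post-intervention assessment being given on completion of coaching, as the Procedures section says. On that reading, neither the conduct of the trial nor its conclusions depend on which year is right.

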### **e) Study Endpoints**

The primary endpoint is participants' treatment decision-making needs, as assessed by the Decisional Conflict Scale (DCS) and a qualitative measure designed to parallel items from the DCS.

We will also assess feasibility of study and intervention procedures by tracking data pertaining to recruitment, retention, and assessment procedures using CONSORT guidelines, and data related to implementation of the intervention (e.g., fidelity, number and duration of intervention meetings by participant, implementation barriers and facilitators). These data will be collected from fidelity checklists and contact notes completed by the decision coach.

Acceptability of the study intervention will be assessed via quantitative and qualitative questions about participants' level of satisfaction and experiences with the intervention. Exploratory, secondary outcomes/measures include:

Multidimensional Scale of Perceived Social Support: This scale assesses perceived adequacy of support in the following areas: family, friends, and significant other.

Control Preference Scale: This measure assesses patients' preferences for participation in treatment decision-making.

Perceived Involvement in Care Scale: This scale measures perceived clinician facilitation of patient involvement in decision-making, perceived level of information exchange between patient and provider, and perceived level of the patient's own involvement in medical decision-making.

Birchwood Insight Scale: A scale that measures dimensions of insight in the following areas: ability to re-label symptoms, awareness of mental illness, and recognition of a need for treatment.

Recovery Assessment Scale: This scale measures personal recovery and consists of 5 factors: personal confidence and hope, willingness to ask for help, goal and success orientation, reliance on others, and not being dominated by symptoms.

Internalized Stigma of Mental Illness Scale (ISMI): This measure is designed to assess individuals' experience of stigma related to mental illness.

Empowerment Scale: A scale that measures empowerment, control, self-determination, and decision making in the recovery process.

Decision-Self-Efficacy Scale: This measure assesses confidence in making an informed treatment choice.

Service Use and Resources Form (SURF-M): SURF-M is a self-report measure that assesses service use over the past month from diverse sources of inpatient and outpatient care including antipsychotic medication with daily doses, and other psychotropic and non-psychotropic medication.

Brief Adherence Rating Scale (BARS): This scale assesses antipsychotic medication adherence of patients in outpatient settings.

Intent to Attend Measure: A measure that assesses participants' intention to engage in the coordinate specialty care program.

Service Engagement Scale: A clinician-rated scale that measures engagement in community mental health services.

Working Alliance Inventory: This 36-item scale assesses the strength of the therapeutic alliance with participants' therapists in three domains: agreement on goals, assignment of tasks, and the development of bonds.

Intentional Peer Support Scale: A scale designed to measure the relationship between the decision coach and patient.

Satisfaction with Decision Scale: This scale assesses a patient's satisfaction with a health care decision.

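### The past-month SURF-M window can include decision-coaching meetings at post-intervention but not at baseline, so the change in outpatient contacts may be inflated if participants report them

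*Combined protocol and SAP*

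**What the plan says.** Section 11(e), Study Endpoints, lists SURF-M among the exploratory, secondary measures: "SURF-M is a self-report measure that assesses service use over the past month". The same entry names both inpatient and outpatient care as sources and also covers medication. Table 1 schedules the form at baseline and at post-intervention.

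The timing of those two visits is set in the Procedures section. At the start, "Participants will complete a baseline assessment with the research assistant prior to engaging in the decision support intervention". At the end, "Upon completion of the intervention, participants will complete a post-intervention assessment with the research assistant". No number of days is given between the last coaching meeting and that interview.

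On the coaching itself, section 11(d), Study Timelines, says that "they will participate in the study intervention on a weekly or biweekly basis for approximately 1-3 months", with meetings of 45-60 minutes. The Procedures section gives a somewhat different duration: "it is expected that participation in the intervention will last approximately 3 months". Section 8 says "Participants will receive the study intervention at the CSC program from which they were recruited", and section 6 says that the coach is a peer specialist or another member of that program's staff.

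Section 11(f), Data Management, applies paired t-tests to the quantitative pre-post measures in general. The SAP names a paired t-test only for the DCS Factors Contributing to Uncertainty subscale and does not mention SURF-M. Neither text says whether a coaching meeting counts as service use. The number and duration of coaching meetings are recorded for each participant, but as feasibility data.

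**The concern.** The same one-month question is asked over two windows that differ by design. The baseline window cannot contain a coaching meeting. The post-intervention window may contain several. These meetings are regular, last most of an hour, concern treatment, and are held with staff of the program where the participant is already a client. Someone asked about outpatient contacts in the past month could reasonably include them.

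If so, the intervention is counted as part of its own outcome. The study has a single group, so no comparison arm would show the same artefact and allow it to be removed. A mechanical rise in contacts could not be told apart from a real rise in use of other care. The abstract names engagement in the program as a secondary outcome, and the pilot is meant to inform a larger study, so a rise in outpatient contacts could be taken as a sign of engagement.

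**Working it through.** The plan gives no figure to reproduce. It states no SD, effect size or power for SURF-M, and N = 20 is said to be pragmatic.

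**Step 1. Coaching contacts in each window.**
- Inputs from the documents: a past-month window; coaching weekly (every 7 days) or biweekly (every 14 days); no coaching before baseline.
- Assumptions: a month is 30 days, and *g* is the number of days from the last meeting to the interview.
- Baseline window: 0 contacts.
- Post-intervention window: (30 − *g*) / interval.

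| Gap *g* (days) | Weekly | Biweekly |
|---|---|---|
| 0 | 30/7 = 4.3 | 30/14 = 2.1 |
| 7 | 23/7 = 3.3 | 23/14 = 1.6 |
| 14 | 16/7 = 2.3 | 16/14 = 1.1 |
| 21 | 9/7 = 1.3 | 9/14 = 0.6 |
| 30 | 0 | 0 |

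The upper end is therefore about 4 (weekly) or 2 (biweekly) contacts. The two stated durations give the same result, because a course of at least about one month fills the window when *g* is near 0. They should still be reconciled.

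**Step 2. From contacts held to bias in the change.** Let *k* be the meetings in the window, *c* the share that participants report as outpatient contacts, and *s* the ordinary contacts that coaching displaced. With no other change in care, the recorded change is *c·k* − *s*. It reaches +4 or +2 only if *c* = 1, *s* = 0 and *g* is about 0. For example, weekly coaching with half the meetings reported and none displaced gives 0.5 × 4 = +2. If *c* = 0, nothing is inflated. The documents give neither *c* nor *s*.

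**Step 3. What such a shift could do to a paired t-test (illustration).** Assume a count of outpatient contacts is analysed, 20 complete pairs, two-sided 0.05, and no true change in other care. The chance of significance comes from the noncentral t distribution with 19 degrees of freedom and noncentrality (shift/SD) × √20. For +2 and SD 3 the noncentrality is 0.667 × 4.472 = 2.98.

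| Assumed SD of change | +2 contacts | +4 contacts |
|---|---|---|
| 3 | 81% | over 99% |
| 4 | 57% | 99% |
| 6 | 29% | 81% |
| 8 | 19% | 57% |
| 10 | 14% | 40% |

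The nominal rate would be 5%. Fewer complete pairs, partial reporting, displacement or a gap before the interview would all lower these figures.

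**The case against.** The strongest objection is that the mechanism depends on an instrument the documents do not show. They describe SURF-M in one entry, with no items, instructions or scoring. The form may already leave such meetings out, or the research assistant conducting the interview may do so. The plan also defines no outpatient-contact score, so the t-test in the illustration is on a constructed outcome. This stands, and it is why the point is a risk and not a demonstrated error.

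A reader might go further and infer that the study will show a spurious gain in engagement, always in the favourable direction. The documents do not support that:
- They nowhere say that higher SURF-M use is better, and the form also covers inpatient care.
- Engagement has its own measures, the clinician-rated Service Engagement Scale and the Intent to Attend Measure.
- The coach may be someone the participant already sees, so coaching may replace ordinary contacts and leave a smaller net rise or none.

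It is also fair to say that significance is not a decision rule in a pilot sized on practical grounds, that the SD range has no source in the documents, and that meeting counts will in any case be available as feasibility data. That last point helps only in part. Seeing coaching exposure beside a service-use result does not tell the reader how much of it was reported on SURF-M.

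What survives is the unequal pair of windows and the lack of any stated rule for coaching contacts. Once the two kinds of contact are mixed in a self-report, the single-group comparison cannot separate them.

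**Conclusion.** The point holds as a conditional measurement risk for one part of one exploratory outcome. If participants report coaching meetings as outpatient contacts, the pre-post change in those contacts is inflated by up to about 2 per participant with biweekly coaching or 4 with weekly coaching. The amount shrinks with any gap before the interview, with partial reporting, and with displacement of other contacts. The probabilities of a significant result are illustrative only, since they rest on an assumed SD, full reporting and 20 complete pairs.

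The SURF-M inpatient and medication items are not affected, and neither is the primary DCS endpoint. The change is worth making because it is nearly free beforehand, whereas the mixture cannot be reliably undone afterwards.

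**What to change.** 1. When SURF-M is given at post-intervention, have the research assistant tell participants to leave out decision-coaching meetings, but to keep ordinary visits with the same staff member. Alternatively, record coaching meetings on a separate line. If the form already excludes them, say so in the protocol.
2. Add one SAP sentence defining the outpatient service-use outcome as contacts excluding decision coaching.
3. Report coaching contacts separately, as intervention exposure, from the coach's contact notes. If coaching displaces ordinary visits, the outcome in item 2 will fall, and this report lets the reader see why.
4. Use subtraction of logged coaching contacts only as a sensitivity check. It over-corrects when the participant did not report the meetings and can produce negative counts. It also needs meeting dates, whereas the endpoints section mentions only number and duration.

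The cost is one instruction on the form and one sentence in the SAP; contact notes are already kept. The small downside is that some participants may misclassify visits with a staff member who is also their coach. A separate line for coaching meetings would at least make that visible.
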